10.2 DATA ANALYSIS

Subjects completing the study protocol will be defined as infected or un-infected (neutralising antibody to RV-16 at 6 weeks post inoculation at a titre $<1:4$ and no detection of RV-16 by qPCR in nasal lavage, sputum or BAL at any point after inoculation). Only subjects with confirmed rhinovirus infection will be included in statistical analysis.

Quantitative assessments of symptom scores, lung function, exhaled nitric oxide (FeNO), airway hyperresponsiveness (histamine challenge, PC_{20}), virus load, inflammatory cell numbers and inflammatory markers will be compared within subjects to determine differences between baseline and during infection. Within-subject differences will be analyzed using ANOVA and 2-tailed paired Student's t-tests or Wilcoxon signed rank test as appropriate.

Differences between the patients taking OC459 and placebo group will be analyzed using unpaired parametric or non-parametric analysis as appropriate at each phase of the study. Correlations between (but not limited to) the following will be examined using Spearman's rank correlations to investigate possible causal relationships:

- illness severity (symptoms, lung function, airway hyperresponsiveness)
- virus load
- inflammatory cell counts
- inflammatory markers
- gene expression

Data and all appropriate documentation will be stored for a minimum of 10 years after the completion of the study, including the follow-up period.

11 QUALITY CONTROL AND QUALITY ASSURANCE PROCEDURES

11.1 RISK ASSESSMENT AND MONITORING

Regular monitoring will be performed by the Joint Research Compliance Office (JRCO) Clinical Trial Monitor at Imperial College, who will monitor the study regularly based on a completed risk assessment by the sponsor. The study will be monitored according to Good Clinical Practice (GCP). Data will be evaluated for compliance with the protocol and accuracy in relation to source documents. Following written standard operating procedures, the monitors will verify that the clinical trial is conducted and data are generated, documented and reported in compliance with the protocol, GCP and the applicable regulatory requirements.

11.2 SERIOUS BREACHES

The Medicines for Human Use (Clinical Trials) Regulations contain a requirement for the notification of "serious breaches" to the MHRA within 7 days of the Sponsor becoming aware of the breach.

A serious breach is defined as "A breach of GCP or the trial protocol which is likely to affect to a significant degree –

- (a) the safety or physical or mental integrity of the subjects of the trial; or
- (b) the scientific value of the trial".

In the event that a serious breach is suspected the Sponsor must be contacted within 1 working day. In collaboration with the C.I., the serious breach will be reviewed by the Sponsor and, if appropriate, the Sponsor will report it to the REC committee, Regulatory authority and the NHS host organisation within seven calendar days.

11.3 REPORTING

The Chief Investigator shall submit once a year throughout the clinical trial, or on request, an Annual Progress Report to the Research Ethics Committee, host organisation, and Sponsor. In addition, an End of Trial notification and final report will be submitted to the MHRA, the REC, host organisation and Sponsor.

12 REGULATORY ISSUES

12.1 CTA

Clinical Trials Authorisation will be obtained from the UK Competent Authority, the Medicines & Healthcare products Regulatory Agency (MHRA), prior to starting recruitment.

12.2 ETHICS APPROVAL

The Chief Investigator will obtain approval from a Research Ethics Committee. The study must be submitted for Site Specific Assessment (SSA) at each participating NHS Trust. The Study Coordination Centre will require a copy of the Trust R&D approval letter before accepting participants into the study. The study will be conducted in accordance with the recommendations for physicians involved in research on human subjects adopted by the 18th World Medical Assembly, Helsinki 1964 and later revisions.

12.3 CONSENT

Consent to enter the study must be sought from each participant only after a full explanation has been given, an information leaflet offered and time allowed for consideration. Signed participant consent should be obtained. The right of the participant to refuse to participate without giving reasons must be respected. After the participant has entered the trial the clinician remains free to give alternative treatment to that specified in the protocol at any stage if he/she feels it is in the participant's best interest, but the reasons for doing so should be recorded. In these cases the participants remain within the study for the purposes of follow-up and data analysis. All participants are free to withdraw at any time from the protocol treatment without giving reasons and without prejudicing further treatment.

12.4 CONFIDENTIALITY

Participants' identification data will be required for the registration process. The Study Coordination Centre will preserve the confidentiality of participants taking part in the study and is registered under the Data Protection Act.

12.5 INDEMNITY

Imperial College London holds negligent harm and non-negligent harm insurance policies which apply to this study.

12.6 SPONSOR

Imperial College London will act as the main Sponsor for this study. Delegated responsibilities will be assigned to the NHS trusts taking part in this study.

12.7 FUNDING

The Medical Research Council (MRC) are funding this study.

12.8 EXPENSES AND BENEFITS

Participants in the study will have their travel expenses refunded. They will also be given a donation of £1,500 to compensate for time and inconvenience of taking part in the study. If subjects drop out, they will receive a pro rata amount: £300 if after the first bronchoscopy; £500 if after rhinovirus inoculation; £1,000 if after the second bronchoscopy; and £1,500 on completion.

12.9 AUDITS AND INSPECTIONS

The study may be subject to inspection and audit by Imperial College London under their remit as Sponsor, the Study Coordination Centre and other regulatory bodies to ensure adherence to GCP.

13 TRIAL MANAGEMENT

The day-to-day management of the trial will be co-ordinated by [name] (Clinical Research Fellow), with close support from [name], [name], and [name].

A Trial Steering Committee will be appointed and will be responsible for overseeing the progress of the trial. This will incorporate the activities of a Data Monitoring Committee. The Trial Steering Committee will include members of the research team, a patient representative, and a consultant in Respiratory medicine independent of the study group. An independent statistician will be invited as required. The Trial Steering Committee will meet every six months (and additionally on an *ad hoc* basis as required) to review the data, oversee the safety of subjects in the trial, and ensure that no events have occurred that would slow the progression of the trial. The minutes from these meetings will be stored in the Trial Management Folder.

14 PUBLICATION POLICY

It is expected that after analysis the data from this study will be widely distributed in the medical and scientific community. Facilitated with presentations at local, national and international meetings, we hope to publish widely in the medical literature. In addition, we have an excellent media department at Imperial College and publicise research that has public interest when it is published.

Appendix B. Participant daily diary card record

NAME Please score symptoms in the boxes as shown: 0 = no symptoms 1 = mild 2 = moderate 3 = severe

Date																				
Sneezing																				
Runny nose																				
Blocked or stuffy nose																				
Sore throat or hoarse voice																				
Headache or face pain																				
Generally unwell																				
Chill, fever or shivery																				
Cough																				
Total cold score																				
Cough on waking																				
Wheeze on waking																				
Daytime Cough																				
Daytime Wheeze																				
Daytime chest tightness																				
Daytime breathlessness																				
Nocturnal cough, wheeze, breathlessness																				
Total Chest score																				
Medications (name and dose)																				
1.																				
2.																				
3.																				
Spirometry: Peak Flow am																				
FEV ₁ am																				
Peak Flow pm																				
FEV ₁ pm																				

Appendix C. Asthma Control Questionnaire (ACQ)

1. On average, during the past week, how often were you woken by your asthma during the night?

- 0 Never
- 1 Hardly ever
- 2 A few minutes
- 3 Several times
- 4 Many times
- 5 A great many times
- 6 Unable to sleep because of asthma

2. On average, during the past week, how bad were your asthma symptoms when you woke up in the morning?

- 0 No symptoms
- 1 Very mild symptoms
- 2 Mild symptoms
- 3 Moderate symptoms
- 4 Quite severe symptoms
- 5 Severe symptoms
- 6 Very severe symptoms

3. In general, during the past week, how limited were you in your activities because of your asthma?

- 0 Not limited at all
- 1 Very slightly limited
- 2 Slightly limited
- 3 Moderately limited
- 4 Very limited
- 5 Extremely limited
- 6 Totally limited

4. In general, during the past week, how much shortness of breath did you experience because of your asthma?

- 0 None
- 1 A very little
- 2 A little
- 3 A moderate amount
- 4 Quite a lot
- 5 A great deal
- 6 A very great deal

5. In general, during the past week, how much of the time did you wheeze?

- 0 Not at all
- 1 Hardly any of the time
- 2 A little of the time
- 3 A moderate amount of the time
- 4 A lot of the time
- 5 Most of the time
- 6 All the time

6. On average, during the past week, how many puffs of short-acting bronchodilator (eg. Ventolin) have you used each day?

- 0 None
- 1 1-2 puffs most days
- 2 3-4 puffs most days
- 3 5-8 puffs most days
- 4 9-12 puffs most days
- 5 13-16 puffs most days
- 6 More than 16 puffs most days

7. FEV₁ pre-bronchodilator:

- 0 >95% predicted
- 1 95-90%
- 2 89-80%
- 3 79-70%
- 4 69-60%
- 5 59-50%
- 6 <50% predicted

2.1. Primary Objective

To assess the impact of OC459 on Total Lower Respiratory Tract Symptoms Score after rhinovirus infection (sum of daily scores day 0 to day 14)

2.2. Secondary Objectives

- To assess the impact of OC459 on other clinical and laboratory parameters during rhinovirus infection in asthma:
 - Health status
 - Lung function
 - Airway inflammation
 - Airway hyper-responsiveness
 - Viral load
- To determine the mechanism of action of OC459, by assessing the impact of OC459 on the following during rhinovirus infection:
 - Eosinophil recruitment
 - Recruitment of other immune cells (e.g. ILC2, Th2) implicated in the prostaglandin D2 / type 2 inflammatory pathway to the airways and/or airway mucosa
 - Release of inflammatory mediators implicated in the prostaglandin D2 / type 2 inflammatory pathway (e.g. the type 2 cytokines IL-4, IL-5, IL-13)
- To assess the safety of OC459
- Exploratory - To assess whether OC459 is able to restore deficient innate antiviral responses in asthma

3. Study Endpoints

3.1. Primary Endpoint Variable

- Total Lower Respiratory Tract Symptoms Score after rhinovirus infection (sum of daily scores day 0 to day 14)

3.2. Secondary Endpoint Variables

- To assess the impact of OC459 on other clinical and laboratory parameters during rhinovirus infection in asthma:
 - Upper Respiratory Tract Symptoms Scores from D0 to D14
 - Corrected Lower Respiratory Tract Symptoms Scores from D0 to D14
 - Asthma Control Questionnaire (ACQ-6) scores
 - Spirometry – FEV₁, FVC, PEFR
 - Exhaled nitric oxide (FeNO) levels
 - Provocation concentration [of histamine] producing a 20% fall in FEV₁ (PC₂₀)
 - Viral load (measured by qPCR)
- To determine the mechanism of action of OC459, by assessing the impact of OC459 on the following during rhinovirus infection in asthma:
 - cell counts in sputum and bronchoalveolar lavage (BAL)
 - immune cells (e.g. ILC2, Th2) in BAL, blood and nasal scrapes, measured by flow cytometry
 - immune cells in bronchial biopsies, measured by immunohistochemistry staining
 - soluble mediators in the upper and lower airways, measured by multiplex immunoassay on nasosorption, nasal lavage, bronchosorption and BAL samples
- To assess the safety of OC459
 - Adverse event reporting
 - physical examinations
 - vital signs
 - clinical laboratory parameters
- Exploratory - To assess whether OC459 is able to restore deficient innate antiviral responses
 - Production of antiviral interferons (IFN), e.g. β and λ by cells from blood and bronchial brushings following infection with respiratory viruses *ex vivo*
 - expression of mRNA for interferon and a panel of interferon-stimulated genes in cells from the same *ex vivo* studies

4. Background/Introduction

4.1. Introduction

Asthma is a long-term condition affecting the airways in the lungs, causing symptoms in patients such as breathlessness, wheeze, tightness in the chest and cough. Asthma is the most prevalent chronic respiratory disease, affecting 5-10% of adults with a further 30% of school age children reporting wheeze. Although some children will outgrow their asthma, future prevalence is predicted to rise: the WHO estimate 300 million people worldwide are affected by asthma and that this is likely to increase to 400 million cases over the next 15-20 years [2].

The major morbidity, mortality and health care costs related to asthma are a result of periods of acutely increased symptomatology, called 'exacerbations'. Acute exacerbations of asthma are an enormous problem to adults and children: ~5-10% of asthmatics have been hospitalised with an exacerbation and 60% have had an exacerbation in the previous year. Asthma mortality in the UK is ~1,000 per annum – extrapolated to Europe, this means approximately ~11,000 people die unnecessarily of asthma each year. The financial cost of exacerbations is estimated to be ~50% of total expenditure on asthma care.

As of August 2013, at least 12 CRTH2 antagonists were in active clinical development. Of these, OC459 (Atopix Therapeutics Ltd) had been trialled for the longest duration in a phase 2 study (17 weeks). In total, 637 patients across five published studies have been exposed to OC459, including 482 patients with asthma, with an excellent safety record. OC459 has therefore been chosen for further study from the available CRTH2 antagonists due to its safety profile; there is no reason to think that it is more or less effective than any other CRTH2 antagonist.

In addition, the largest study of OC459 to date suggested that it may be effective in reducing exacerbations: a trend towards reduction in asthma exacerbations was noted, with a 3.8% incidence in the pooled dose groups compared to 7.7% on placebo ($p=0.107$). A dose of 25 mg once daily was as effective as the other doses (100mg twice daily and 200mg once daily) in this study.

Based on the above; this trial is designed to investigate the hypothesis that CRTH2 antagonism can prevent or attenuate the deterioration in symptoms in patients with asthma (i.e. asthma exacerbations) following rhinovirus infection.

4.2. Study Design

This is a randomised, double-blind, placebo-controlled, parallel group phase 2a study which will take place over a 36 month period. On an individual basis, the trial will last for 9 weeks from randomisation.

The trial will be considered complete when the last patient recruited completes the final visit.

4.3. Study Population

English speaking, male or female patients between the age of 18-55 who have had a Clinical diagnosis of asthma for at least 6 months prior to screening will be deemed eligible for the trial if they satisfy the following additional Inclusion Criteria:

- An Asthma Control Questionnaire (ACQ-6) Score >0.75
- Positive histamine challenge test (PC_{20} <8 $\mu\text{g}/\text{ml}$, or <12 $\mu\text{g}/\text{ml}$ and bronchodilator response $\geq 12\%$)
- Worsening asthma symptoms with infection since last change in asthma therapy
- Positive skin prick test to common aeroallergens (e.g. animal epithelia, dust mite)
- Treatment comprising inhaled corticosteroids (ICS) or combination inhaler (Long-Acting Beta Agonist with ICS), with a daily ICS dose of at least 100mcg fluticasone or equivalent.
- Participant is willing for their GP to be informed of their participation.

Patients must also not fall under any of the following exclusion criteria:

- Presence of clinically significant diseases other than asthma (cardiovascular, renal, hepatic, gastrointestinal, haematological, pulmonary, neurological, genitourinary, autoimmune, endocrine, metabolic, neoplasia etc.), which, in the opinion of the investigator, may either put the patient at risk because of participation in the trial, or diseases which may influence the results of the study or the patient's ability to take part in it
- Smoking history over past 12 months.
- Seasonal allergic rhinitis symptoms at screening or during the 3 week run-in (prior to rhinovirus inoculation).
- Asthma exacerbation or viral illness within the previous 6 weeks or during the 3 week run-in (prior to rhinovirus inoculation).
- Current or concomitant use of oral steroids, anti-leukotrienes or monoclonal antibodies.
- Pregnant or breast-feeding women. Patients should not be enrolled if they plan to become pregnant during the time of study.
- Contact with infants <6 months or immunocompromised persons, elderly and infirm at home or at work.
- Subjects who have known evidence of lack of adherence to medications and/or ability to follow physician's recommendations.

Whilst not listed within the trial protocol; an additional test was carried out to assess previous exposure to rhinovirus 16, as evidenced by the presence of serum neutralising antibodies to rhinovirus 16 at screening.

Subjects who meet the relevant criteria and provide informed consent are deemed eligible for randomisation to the trial.

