4 PARTICIPANT ENTRY

4.1 PRE-RANDOMISATION EVALUATIONS

Potential subjects for the study will be recruited from hospital outpatient clinics, GP surgeries, spirometry sessions/clinics, other research projects, and advertisements. They will attend the respiratory clinic at St Mary's Hospital, where the outline of the study will be explained to them and a Participant Information Sheet (PIS) provided. They will be given the opportunity to ask questions and be informed that their participation is voluntary. Subjects may decide they wish to have more time to consider taking part in the study, in which case a follow up appointment will be made, or they may continue with the screening process. When a subject has had enough time to consider their participation in this study, and only when they have agreed to take part, they will be asked to read, sign and date a consent form in the presence of the investigator who will also sign the consent form. A copy will be kept in the research file, a copy given to the patient and a copy put into their medical notes.

After signing a consent form, eligible subjects will undergo screening. Screening involves taking a medical history and examination, lung function testing, a histamine challenge, FeNO levels, skin prick testing, blood tests, a urine pregnancy test, and a chest radiograph to assess suitability against the defined inclusion and exclusion criteria. Blood tests include general screening for underlying illness, specifically full blood count, urea and electrolytes, liver function tests, coagulation, and C-reactive protein (CRP), as well as serology for rhinovirus 16 (RV-16). They will be matched to the inclusion/exclusion criteria, which have been maintained from previous studies using the rhinovirus-induced asthma exacerbation model.

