10 STATISTICS AND DATA ANALYSIS

10.1 SAMPLE SIZE CALCULATION

The sample size determination is based on the following assumptions:

Type I error probability $\alpha = 5\%$

Effect size = $(\mu_1 - \mu_0)/\sigma$, where

μ_i = mean PEP in group i ($i=1$: OC459, $i=0$: placebo),

σ = standard deviation of PEP, and

PEP is primary end-point (=total daily lower respiratory symptom scores over d0 to d14).

Based on a previously completed trial with similar design conducted at the same study site [10], σ is estimated to be 21.15 and the effect size equal to 22.21, yielding $n=15$ evaluable subjects per treatment group at 80% power. This is grossed-up for 80% rhinovirus inoculation success and adjusted for expected drop-outs to yield 22 enrolled patients per treatment group.

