4.4. Sample Size

An overall population size of 44 asthmatic subjects was based on the following assumptions:

- Type I error probability $\alpha = 5\%$
- Effect size = $(\mu_1 - \mu_0) / \sigma$
 - μ_i = mean PEP in group i ($i=1$: OC459, $i=0$: placebo),
 - σ = standard deviation of PEP
- PEP is primary end-point (=total daily lower respiratory symptom scores over D0 to D14, potential maximum of 315).

Based on a previously completed trial with similar design conducted at the same study site [10], σ is estimated to be 21.15 and the effect size equal to 22.21, yielding $n=15$ evaluable subjects per treatment group at 80% power. This is grossed-up for 80% rhinovirus inoculation success and adjusted for expected drop-outs to yield 22 enrolled patients per treatment group.

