4.6. Randomisation

Subjects who meet the relevant criteria and provide informed consent will be randomised to either OC459 or placebo in a 1:1 ratio. Randomisation will occur at a baseline visit after the screening visit(s), and will be in blocks of four in order to balance the number of patients allocated to each treatment group. A dummy unblinded randomisation list (taking into account the blocking requirements) will be generated by the trial statistician and tested. Once tested, a statistician working independent to the trial will create the final list for entering into the study database. This file will be password protected, with unblinding instructions provided by the database development team to the investigators.

At randomisation, the database will be interrogated and each new subject assigned the next sequential randomisation item on the list. The unblinded randomisation list will also be provided to the manufacturer, Atopix Ltd, in order to label IMP/placebo appropriately prior to dispensing to pharmacy. Thus the investigators, pharmacy and subjects will all be blinded.

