7.2. Primary Analysis

Uncorrected lower respiratory symptom scores collected from D0 to D14 will be aggregated to create an overall total for each patient. Where patient scores are missing, data will be imputed based upon rules set within Section 7.5. Patients missing $\geq 20\%$ of score data will be excluded from any additional per-protocol analyses.

Data will be presented using summary statistics per treatment group and will include median and interquartile range (IQR). A supplementary plot showing individual measurements for both groups with a box & whisker overlay showing median and IQR will be produced.

Primary analysis to test for difference between the mean aggregated scores of the two treatment groups will be carried out using Mann-Whitney U tests. Differences will be considered significant at $P < 0.05$. All P values are two-sided.

An additional secondary analysis will take place correcting the scores for bronchoscopy-related symptoms. Full methodology will be clarified within Section 7.3.1 below.

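### Screening RV-16 antibody is measured but decides nothing in the listed criteria, so a subject seropositive at entry can be counted as infected on an unchanged titre and dilute the primary comparison

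*SAP*

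**What the plan says.** Protocol 4.1 lists the screening blood tests and adds "as well as serology for rhinovirus 16 (RV-16"). Protocol 9.3 and Table 1 place the serology at screening and at day 42. Protocol 4.2 and 4.3 contain no criterion on the result.

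SAP 4.3 repeats the criteria, again without one on RV-16 antibody. Directly after the exclusion list it states: "Whilst not listed within the trial protocol; an additional test was carried out to assess previous exposure to rhinovirus 16". It names neutralising antibody at screening as the evidence of exposure, gives no titre and no consequence, and then makes subjects eligible if they meet the relevant criteria.

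Two later rules use antibody. SAP 5.2 admits a subject to the full analysis set (FAS) as infected on either a positive nasal lavage PCR after inoculation or a titre of at least 1:4 at the final visit. It calls the second route seroconversion but does not refer to the screening titre. Protocol 10.2 calls a subject uninfected only if the six-week titre is below 1:4 and no virus was detected.

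On numbers, Protocol 10.1 says: "This is grossed-up for 80% rhinovirus inoculation success and adjusted for expected drop-outs to yield 22 enrolled patients per treatment group". Neither document says which population the 80% describes.

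**The concern.** In a challenge trial, antibody to the challenge strain at entry bears on whether the inoculation produces an infection at all. The plan collects this information before randomisation and then leaves it unused, or used in a way that is not written down.

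Two things follow. A seropositive subject can go through randomisation, two bronchoscopies (days -8 and 5) and inoculation. The infection rule then cannot tell antibody raised by the inoculation from antibody already present, because it looks at one titre only. A subject who entered at 1:4 or above and stayed there passes as infected. Such a subject has had no virus-induced deterioration for the drug to prevent, yet contributes a symptom total to the primary test.

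Nothing later in the plan would reveal or correct this. Randomisation is not stratified on serostatus (SAP 4.6), the primary test is an unadjusted Mann-Whitney (SAP 7.2), and screening RV-16 serostatus is not among the baseline variables in SAP 6.1.

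**Working it through.** **1. The plan's own figure.** Inputs from SAP 4.4: "σ is estimated to be 21.15 and the effect size equal to 22.21" and "yielding $n=15$ evaluable subjects per treatment group at 80% power"; alpha 5%, taken as two-sided because SAP 7.2 says "All P values are two-sided"; allocation 1:1 (SAP 4.6). The 22.21 works only as a raw difference (22.21/21.15 = 1.05 SD).

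- n per arm = 2 × (1.960 + 0.842)² × (21.15/22.21)² = 14.24, rounded up to 15. Reproduced.
- Power at 15 per arm: 82.0% by the normal formula, 79.3% by the t-test.
- Gross-up: 15/0.80 = 18.75. Reaching 22 implies a drop-out of 1 − 18.75/22 = 14.8%, which the documents do not state.

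**2. How the infection rule classifies subjects** (SAP 5.2 with Protocol 10.2):

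| Screening titre | PCR after inoculation | Day-42 titre | Class |
|---|---|---|---|
| below 1:4 | negative | below 1:4 | uninfected |
| below 1:4 | negative | 1:4 or above | infected; the titre has risen |
| 1:4 or above | negative | 1:4 or above, unchanged | infected; nothing has changed |

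The third row is the problem.

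**3. Effect on the evaluable count.** Let s be the share of entrants who are seropositive. Assume 80% infection in seronegatives, and that seropositives are not infected but keep their titre. Evaluable before drop-out = 44 × [0.8(1 − s) + s]:

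- s = 10%: 44 × 0.82 = 36.1
- s = 20%: 44 × 0.84 = 37.0
- s = 30%: 44 × 0.86 = 37.8

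With s = 0 it is 44 × 0.8 = 35.2. The count rises, so a shortfall would not give a warning.

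**4. Effect on power.** The uninfected share of the evaluable set is f = s/[0.8(1 − s) + s]. If these subjects show no treatment effect and the SD stays at 21.15, the difference shrinks to 22.21 × (1 − f). Power = Φ(difference/21.15 × √(15/2) − 1.960).

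| s (entrants) | f (evaluable) | Difference | Power, normal | Power, t |
|---|---|---|---|---|
| 0% | 0% | 22.21 | 82% | 79% |
| 10% | 12.2% | 19.50 | 71% | 68% |
| 20% | 23.8% | 16.92 | 59% | 56% |
| 30% | 34.9% | 14.46 | 47% | 44% |

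If 10, 20 or 30% is instead taken as the share of the evaluable set itself, the difference is 19.99, 17.77 or 15.55 and power is 74, 63 or 52% (normal).

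**5. If such subjects were not counted as infected.** Suppose the 80% applies to seronegatives only and seropositives drop out of the FAS. Evaluable per arm is then 15 × (1 − s) = 13.5, 12.0 or 10.5, with power 78, 73 or 67% (normal). If the 80% already comes from a population with the same serostatus mix, this loss disappears.

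**The case against.** The strongest reply is that SAP 4.3 may record a screen that was applied. The sentence sits between the exclusion list and the statement of eligibility, and Protocol 4.1 says screening tests assess suitability. The words about not being listed may mean only that the test is not listed as a criterion. This stands as an ambiguity: the text does not prove that seropositive subjects were admitted. It does not remove the point, because a rule that was applied still needs its titre and its timing written down.

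Second, every share used above is assumed. That also stands; the figures are a range, not an estimate.

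Three stronger readings are tempting, and the documents do not support them:

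- A reader might infer that the 80% makes no allowance for seropositive entrants. Its source population is not given, it already leaves room for 20% uninfected, and Protocol 4.1 says the criteria were carried over from earlier studies with this model.
- A reader might infer that such subjects are immune. SAP 4.3 speaks only of exposure, and no protective titre is given.
- A reader might infer that the required 30 evaluable subjects would be missed. With an assumed 20% infection rate in seropositives, 44 × [0.8(1 − s) + 0.2s] gives 32.6, 29.9 and 27.3 infected at 10, 20 and 30% seropositive. But SAP 5.2 counts retained titres as infection, so the evaluable number moves the other way (step 3).

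**Conclusion.** The gap is in the text. RV-16 antibody is measured before randomisation, no listed criterion uses it, SAP 4.3 misdescribes the protocol, and the single-titre rule in SAP 5.2 and Protocol 10.2 can class an uninfected subject as infected. The consequence is a diluted primary comparison that the evaluable count would not show.

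The size cannot be determined from the documents. Power of about 71, 59 or 47% at 10, 20 or 30% seropositive entrants rests on five assumptions: 80% infection in seronegatives, no infection in seropositives, titres that persist to day 42, no treatment effect in those subjects, and an unchanged SD. It also approximates the Mann-Whitney test by a comparison of means. Any infection among seropositives, or titres falling below 1:4, would make the loss from this route smaller. This is a worthwhile and inexpensive improvement, not a demonstrated failure of the design.

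**What to change.** - **Entry criterion.** Make screening RV-16 serostatus explicit in Protocol 4.3 and SAP 4.3. The 1:4 cut-off that the documents already use for positivity at the final visit is the natural choice; using it at entry is a decision to be stated as such. Require the result before randomisation at day -21.
- **SAP 4.3.** Reword the sentence to say that the test is in the protocol and how its result was used. Do not simply delete it, since it may be the only disclosure of a screen applied in practice.
- **The 80%.** State the population it comes from and whether it refers to seronegative entrants.
- **If enrolment is complete**, as the past tense in SAP 4.3 may suggest: report screening serostatus by arm. In subjects already at 1:4 or above at screening, do not count the day-42 titre as infection unless PCR is positive or the titre has risen. Add a seronegative-only sensitivity analysis of the primary endpoint.

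Cost: no new test, since the sample is already taken at screening. Before enrolment ends, the cost is more screen failures and a wait for the titre. Afterwards, it is slightly fewer subjects in the FAS.
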